5.15.2.2. Pancreatitis

The incidence of acute or chronic pancreatitis will be summarized descriptively for each treatment group separately for investigator-reported and adjudicated events from baseline to Week 26, from baseline to Week 52. The individual patients with this event will be listed along with lab tests, including lipase, amylase, and p-amylase.

5.15.2.3. Thyroid C-Cell Hyperplasia and C-Cell Neoplasms

The incidence of all types of thyroid tumors/neoplasms (benign and malignant) including C-cell hyperplasia will be summarized by each treatment group from baseline to Week 26, baseline to Week 52. The incidence of TEAEs associated with all types of thyroid tumors/neoplasms including C-cell hyperplasia will be reported for each treatment group from baseline to Week 26, baseline to V801. The individual patients with this event will be listed along with the laboratory tests, including calcitonin.

For calcitonin, summaries and analysis for changes from baseline and treatment emergent abnormal values will be provided as well as listing of abnormal values.

5.15.2.4. Nausea and Vomiting

Nausea and vomiting are the most common AEs reported in patients treated with dulaglutide from baseline to Week 26 and from baseline to Week 52. Summaries for onset (first incidence), duration, and severity of nausea and vomiting will be provided descriptively. Incidence of nausea and vomiting will be summarized using Fisher's exact test.

5.15.2.5. Allergic, Hypersensitivity, and Injection Site Reactions

Patients experiencing allergic, hypersensitivity, and injection site reactions will be listed and summarized for each treatment group from baseline to Week 26 and from baseline to Week 52 using Fisher's exact test.

5.15.2.6. Renal Impairment

The incidence of investigator-reported renal impairment (including renal failure) will be summarized for each treatment group from baseline to Week 26 and baseline to Week 52 by MedDRA terms.

5.15.3. Anti-Drug Antibodies (Immunogenicity)

If dulaglutide ADAs are detected, listings of antibody titers, antibody types, and HbA1c values by patient will be provided. A summary of incidence of treatment-emergent antibodies by antibody types will also be presented from baseline to Week 26 and baseline to Week 52. The presence of treatment-emergent ADAs is defined as a change from negative at baseline to positive at endpoint with antibody titer greater or equal to 1:4 or a positive at baseline to a positive at endpoint with greater or equal to a 4-fold increase. That is, if a positive antibody titer changes from 1:2 at baseline to 1:8 at endpoint, it is considered treatment emergent. Treatment-emergent ADAs may be further characterized and/or evaluated for their ability to neutralize the activity of dulaglutide.

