6.2. Secondary Objectives

The secondary objectives of the study are to assess the efficacy, safety, PK and pharmacodynamics (PD) in patients.

The key secondary efficacy objectives are to compare the dulaglutide 0.75 mg and dulaglutide 1.5 mg arms (individually and pooled) to placebo with respect to the following parameters:

- Change in HbA1c between baseline and Week 26 (individual doses only)
- Change in fasting blood glucose (FBG) between baseline and Week 26
- Percentage of patients with HbA1c <7.0% at Week 26
- Change in body mass index (BMI) between baseline and Week 26

The other secondary efficacy objectives are to assess the 2 dulaglutide treatment groups (individually and pooled) with respect to the following parameters:

- Change in HbA1c between baseline and Week 52
- Change in FBG between baseline and Week 52
- Percentage of patients with HbA1c <7.0% at Week 52
- Change in BMI between baseline and Week 52

The secondary safety objectives are to compare the dulaglutide 0.75 mg and dulaglutide 1.5 mg arms (individually and pooled) to placebo with respect to the following parameters at 26 weeks, and to assess the following parameters in the dulaglutide 0.75 mg and dulaglutide 1.5 mg arms (individually and pooled) at Week 52:

- Glucose management-related safety assessed by the incidence of self-reported hypoglycemic events and the incidence of patients requiring rescue for severe, persistent hyperglycemia
- Pancreatic safety assessed by the incidence of cases of pancreatitis confirmed by adjudication and the effect on pancreatic enzymes
- Thyroid-related safety assessed by the incidence of cases of thyroid treatment-emergent adverse events (TEAEs) and effect on serum calcitonin
- Immune system-related safety, including the incidence of dulaglutide anti-drug antibodies (ADAs), and the incidence of allergic, hypersensitivity, and injection site reactions.

The secondary PK/PD objective is:

- Characterization of the PK of dulaglutide and the relationship between dulaglutide exposure and key safety and efficacy measures.

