- o Includes both pre- and postdose blood draws. At Week 13 (Visit 6), one PK sample is to be taken predose and then study drug should be administered. Later in the visit, one PK sample should be taken between 1 to 12 hours after administration of the Week13 dose. At Week 26 (Visit 9), the PK sample is to be taken predose. At Week 39 (Visit 13), the PK sample can be taken up to 2 days postdose. At Week 52 (Visit 16), the PK sample can be taken at any time during the visit. At Week 56 (Visit 801) and early discontinuation, the sample can be taken at any time during the visit.
- p When a PK sample is drawn, an ADA sample should also be drawn at the same time or within 30 minutes of the PK sample (see footnote n), with the exception of the randomization visit, where an ADA sample is drawn but not a PK sample.

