5.2. General Considerations

Statistical analysis of this study will be the responsibility of Lilly or its designee. Any change to the data analysis methods described in the protocol will require an amendment ONLY if it changes a principal feature of the protocol. Any other change to the data analysis methods described in the protocol, and the justification for making the change, will be described in the SAP or the CSR. Additional exploratory analyses of the data may be conducted as deemed appropriate.

All analyses will be conducted under the guidance and approval of Lilly statisticians.

The treatment groups mentioned in this document are dulaglutide (Dula) 1.5 mg and 0.75 mg (pooled); Dula 1.5 mg; Dula 0.75 mg; and Placebo during the double blinded period (randomization to Week 26) unless otherwise specified. Placebo becomes Placebo/Dula 0.75 mg during the open label period (Week 26 to Week 52) while the other treatment groups are unchanged.

For the purposes of tables, figures, and listings (TFLs), up to Week 26 the treatment groups will be All Dula (pooled dulaglutide doses); Dula 1.5; Dula 0.75; and Placebo. Placebo will be the reference treatment across all statistical reports whenever the treatment effect is compared between All Dula and Placebo, Dula 1.5 and Placebo, and Dula 0.75 and Placebo.

Up to Week 52 or to Week 56 (for selected safety parameters such as ADA at safety follow-up (Visit 801 [V801])), treatment will be expressed in the TFLs as All Dula, Dula 1.5, Dula 0.75, and Placebo/Dula 0.75 representing (Dula 0.75/0.75, Dula 1.5/1.5 pooled), Dula 1.5/1.5, Dula 0.75/0.75, and Placebo/Dula 0.75, respectively. No inference will be made among the treatment groups after Week 26 to Week 52 or from Week 26 to V801. Within-treatment comparisons

between different scheduled visits such as Week 26 and Week 52 for parameters such as HbA1c change (and others) from baseline may be performed.

Generally, V801 data will not be summarized unless otherwise stated, but V801 data may be listed.

Efficacy and safety data will be summarized by each treatment group at each scheduled visit unless otherwise stated.

Six patient populations are defined for the analyses in this study with detailed information listed in [Table GBGC.5.1](#).

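### Treatment-emergent anti-drug antibodies are judged only at an undefined endpoint, so incidence to Week 26 and to Week 52 may be understated

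*SAP*

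**What the plan says.** The secondary safety objectives in Protocol 6.2 cover "Immune system-related safety, including the incidence of dulaglutide anti-drug antibodies (ADAs") along with allergic, hypersensitivity and injection site reactions. They are framed as a comparison with placebo at 26 weeks and an assessment of the dulaglutide arms at Week 52. Protocol 12.2.9.4 asks for a summary of the incidence of treatment-emergent antibodies but does not define the term. SAP 5.15.3 is therefore the only operative rule.

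That section has two limbs, and both depend on endpoint status:

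- Baseline-negative patients: "defined as a change from negative at baseline to positive at endpoint with antibody titer greater or equal to 1:4".
- Baseline-positive patients: "a positive at baseline to a positive at endpoint with greater or equal to a 4-fold increase".

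The worked example keeps the same condition: "if a positive antibody titer changes from 1:2 at baseline to 1:8 at endpoint, it is considered treatment emergent". The output is then described as incidence over a period: "A summary of incidence of treatment-emergent antibodies by antibody types will also be presented from baseline to Week 26 and baseline to Week 52". By-patient listings are also planned: "listings of antibody titers, antibody types, and HbA1c values by patient will be provided".

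On sampling, the footnotes to Protocol Attachment 1 say "When a PK sample is drawn, an ADA sample should also be drawn at the same time" (or within 30 minutes), with an extra ADA sample at randomization. PK samples are scheduled at Weeks 13, 26, 39, 52 and 56 and at early discontinuation.

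On follow-up, SAP 5.2 extends the tables, figures and listings to Week 56 "for selected safety parameters such as ADA at safety follow-up (Visit 801 [V801"]). The same section says that Visit 801 data are generally not summarized unless stated otherwise.

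**The concern.** An incidence over a period should count every patient who becomes treatment-emergent at any time in it. The rule in SAP 5.15.3 looks at one visit at the end. If endpoint is the Week 26 or Week 52 sample, intermediate samples that were collected and assayed cannot make a patient a case. Within a given window, the endpoint count can equal the any-time count but cannot exceed it, so any error makes the drug look less immunogenic than it was.

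The rule also differs from the SAP's handling of other safety data. SAP 5.15.1 counts an adverse event as treatment-emergent if it is new or worse at any time after first dosing. The shift tables in SAP 5.15.8 include maximum post-baseline values. No reason is given for treating ADA differently.

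**Working it through.** The documents give no ADA rate, so there is no planned figure to reproduce. The only arithmetic in SAP 5.15.3 is the titer example: 8 / 2 = 4, a 4-fold rise, which meets the threshold. The example and the rule agree.

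**Which outcomes the rule counts.** Take a baseline-negative patient with every scheduled sample present. Call a sample positive if it meets the 1:4 limit, and take endpoint as the last scheduled sample in the window.

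- *Baseline to Week 26 (samples at Weeks 13 and 26).* Patterns with at least one positive: 2² − 1 = 3. Patterns positive at Week 26: 2. Missed: 3 − 2 = 1, the patient positive at Week 13 only.
- *Baseline to Week 52 (samples at Weeks 13, 26, 39 and 52).* Patterns with at least one positive: 2⁴ − 1 = 15. Patterns positive at Week 52: 2³ = 8. Missed: 15 − 8 = 7.
- *Among those 7.* Patterns positive at Week 26 and negative at Week 52: 2² = 4. The other three are Week 13 only, Week 39 only, and Weeks 13 and 39.

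These are counts of patterns, not probabilities. The four Week 26 patterns show a logical problem that does not depend on any rate. Such patients are cases in the 0-26 table and non-cases in the 0-52 table. In the same patients, an incidence from baseline cannot fall as the window lengthens, but under this rule it could.

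**Possible size.** Let p be the proportion who are ever treatment-emergent in the window, and t the share of those who do not meet the rule at endpoint. Then reported incidence = p × (1 − t). Neither p nor t is in the documents, so the values below are assumptions.

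| Assumed p | t = 0 | t = 25% | t = 50% | t = 75% |
|---|---|---|---|---|
| 2% | 2.0% | 1.5% | 1.0% | 0.5% |
| 5% | 5.0% | 3.75% | 2.5% | 1.25% |
| 10% | 10.0% | 7.5% | 5.0% | 2.5% |

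With 50 patients planned per arm, the pooled dulaglutide group is 2 × 50 = 100 patients, so each percentage point is about one patient.

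**Visit 801.** SAP 5.2 names ADA as a parameter reported to Visit 801. SAP 5.15.3 gives windows only to Weeks 26 and 52. By contrast, SAP 5.15.2.3 states a window to Visit 801 for thyroid events. The two sections on ADA do not match.

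**The case against.** Four points can fairly be made for the plan.

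1. *The objective has fixed time points.* Protocol 6.2 refers to 26 weeks and Week 52, so a baseline-to-endpoint comparison is a defensible reading, and no passage requires any-time counting. This stands as far as it goes. However, SAP 5.15.3 itself calls its output an incidence from baseline to each time point, and an endpoint rule does not deliver that.
2. *Endpoint is undefined for ADA.* SAP 5.2 has a general sentence under which the last nonmissing value becomes the endpoint when the endpoint is missing. It is not tied to ADA. If it were applied, a Week 13 or Week 39 positive with no later sample in the window would count. It would not help a patient whose later sample is present and negative. It also leaves unclear how an early-discontinuation sample is used.
3. *Nothing is lost from the data.* This is correct, because titers are listed by patient. A listing is not an incidence, though, and the table is what will be cited.
4. *The summary is descriptive.* No test on ADA incidence is specified in either ADA section, and the primary result is unaffected. This limits how much weight the point should carry.

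A reader might go further and infer that incidence is certain to be understated. The documents do not support that: the shortfall depends on a transient share they do not give, and it may be nil. A reader might also infer that antibodies first seen at follow-up are ignored. SAP 5.2 expressly foresees ADA reporting at Visit 801, so this is an unreconciled difference between two sections, arising from the reporting windows and not from the word endpoint. Nor does the rule yield a simple prevalence, because unchanged baseline positives are excluded.

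**Conclusion.** The point holds in a limited form. If endpoint means the Week 26 or Week 52 sample, the rule omits from the 0-26 table patients who meet the titer rule only at Week 13. It omits from the 0-52 table those who meet it earlier (Week 13, 26 or 39) but not at Week 52. Reported incidence may then be understated, and 0-52 incidence could fall below 0-26 incidence.

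The size cannot be derived from the documents. It is zero if no antibodies are transient, and otherwise equals the transient share of the true incidence. The conclusion rests on reading endpoint as the scheduled visit closing each window, and on those samples being present. The Visit 801 mismatch is a separate matter of consistency. Overall this is a cheap improvement to a secondary safety summary and no threat to the trial's main conclusions.

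**What to change.** In SAP 5.15.3:

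- Define treatment-emergent ADA on any post-baseline sample within the window. Keep the existing thresholds: titer of at least 1:4 from a negative baseline, or at least a 4-fold rise from a positive one.
- Report that incidence for baseline to Week 26 and baseline to Week 52, with endpoint-positive patients as a subset so that persistence can be seen.
- Say what endpoint means for that subset, and how missing and early-discontinuation samples are handled.
- Separately, reconcile this section with SAP 5.2 on Visit 801, either by adding a window from baseline to Visit 801 or by stating that those results are listed only.

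The cost is SAP wording and minor programming. The samples are already scheduled, so no new samples, visits or patients are needed.

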5.15.4. Malignant Events

The incidence of investigator-reported malignant events will be summarized for each treatment group from baseline to Week 26 and baseline to Week 52 by PT.

5.15.5. Hyperglycemia

The number of patients and the percentage of patients who were rescued due to severe, persistent hyperglycemia will be summarized from baseline to Week 26 and from baseline to Week 52. Fisher's exact test will be applied to compare treatments on the proportion of patients who received rescue therapy due to severe, persistent hyperglycemia. Time to receive the first rescue therapy treatment due to severe, persistent hyperglycemia will be analyzed between treatment groups using the proportional hazard Cox regression model with treatment, stratification factors as fixed effects by excluding HbA1c strata, and adding baseline HbA1c as a covariate. A Kaplan-Meier curve will be plotted for each treatment group on time to first rescue therapy along with the log-rank p-value.

Patients who experienced severe, persistent hyperglycemia and received rescue therapy will be listed.

5.15.6. Vital Signs

All vital signs will be listed using the randomized population.

The change from baseline for sitting systolic and diastolic blood pressures and heart rate (HR) (Table GBGC.5.2) will be analyzed using an MMRM model as described in Section 5.2 using all available post first-dosing scheduled visit data up to Week 52. There will be no multiplicity adjustments for analyses of vital signs. Corresponding figures may be presented.

The incidence of patients with select abnormal vital sign measurements will be summarized from baseline to Week 26 and from baseline to Week 52.

Table GBGC.5.2. Thresholds for Determining Abnormal Systolic Blood Pressure, Diastolic Blood Pressure, and Pulse Rate

Parameter (unit)	Low	High
Systolic BP (mm Hg)	≤ 85 and decrease ≥ 20 (10-11 years old) ≤ 90 and decrease ≥ 20 (≥ 12 years old)	≥ 126 and increase ≥ 20 (10-11 years old) ≥ 136 and increase ≥ 20 (12-14 years old) ≥ 140 and increase ≥ 20 (≥ 15 years old)
Diastolic BP (mm Hg)	≤ 50 and decrease ≥ 10 (≥ 10 years old)	≥ 82 and increase ≥ 10 (10-11 years old) ≥ 86 and increase ≥ 10 (12-14 years old) ≥ 90 and increase ≥ 10 (≥ 15 years old)
Pulse rate (bpm)	<60 and decrease ≥ 25 (10-11 years old) <50 and decrease ≥ 15 (≥ 12 years old)	>140 and increase ≥ 25 (10-11 years old) >120 and increase ≥ 15 (12-14 years old) >100 and increase ≥ 15 (≥ 15 years old)

Abbreviations: BP = blood pressure; bpm = beats per minute.

5.15.7. *Electrocardiograms*

A listing of the ECG measurements (HR, PR, RR, QRS, QT, and corrected QT [QTc]), and abnormal selected ECG parameters will be produced in all randomized population separately.

Descriptive statistics for the actual measurements and change from baseline, by treatment arm and scheduled visit (9 and 16), will be performed for selected ECG parameters using ITT population. The parameters that will be included in the summary and analysis with MMRM model described in Section 5.2 are HR, RR, PR, and QRS intervals.

QT Fridericia's and Bazett's corrections will be used to correct the QT interval using the formulas below:

$$QTcF = QT/RR^{1/3}$$

$$QTcB = QT/RR^{1/2}$$

A MMRM for QT, QTcF, QTcB change from baseline will be analyzed using MMRM. In this model, RR change from baseline and corresponding baseline QT will be fitted as covariates with treatment, insulin use ("yes" versus "no"), metformin use ("yes" versus "no"), baseline HbA1 as strata, visit, and treatment-by-visit as fixed effects. All analysis results related to QTcB are not intended for the CSR but for publication only.

For quantitative ECG variables, summaries and analyses of treatment-emergent abnormal values, and of medical query: any term in arrhythmia-related investigations and signs and symptoms will be generated separately.

Selected thresholds for HR, PR interval, and QTc interval are shown in Table GBGC.5.3 and will be summarized clinically relevant abnormal values for these variables from baseline to Week 26 and from baseline to Week 52.

Table GBGC.5.3. Thresholds for HR, PR Interval, and QTc Interval

ECG Variable (unit)	Threshold
QTcB, QTcF actual measurement (msec)	>460 (≤ 15 yrs), >450 (male, ≥ 16 yrs), >470 (female, ≥ 16 yrs) >500
QTcB, QTcF change from Baseline (msec)	>30, >60, >75
ECG heart rate (bpm)	Refer to pulse rate in Table GBGC.5.2
PR interval (msec)	<120 ≥ 220

Abbreviations: bpm = beats per minute; ECG = electrocardiogram; HR = heart rate; yrs = years.

5.15.8. Analysis of Laboratory Analytes

All laboratory measurements (including scheduled and unscheduled) will be listed using all randomized population. A listing of patients with treatment-emergent abnormal laboratory, with the normal ranges and potentially clinically relevant reference limits for all laboratory tests, with serum calcitonin levels suggestive of thyroid C-cell abnormalities, will be listed separately. For certain labs, age-dependent reference ranges will be used as appropriate.

Descriptive summary statistics will be presented for sodium, potassium, calcium, and glucose random at each scheduled visit in raw data and change from baseline without formal statistical analysis.

For each continuous laboratory measurement listed below, the change from baseline will be summarized for each treatment. The summary statistics include number of patients, mean, SD, minimum, Q1, median, Q3, and maximum. These analytes will be analyzed using ANOVA on the ranks, with treatment as a fixed effect. LOCF will be used to impute missing postbaseline values. Wilcoxon signed-rank test will be used to compare baseline and each post-baseline visit within the same treatment:

- Pancreatic enzymes (lipase, amylase, P-amylase)
- Liver test panel (ALT, AST, CK, alkaline phosphatase, total bilirubin, direct bilirubin, albumin)
- Renal (eGFR, albumin-to-creatinine ratio [ACR], serum creatinine, serum BUN, serum cystatin C, uric acid)
- Serum lipids (total cholesterol, HDL cholesterol, LDL cholesterol, triglycerides)
- Hormone-related safety assessed by the effect on serum
 - Prolactin
 - Insulin-like growth factor-1

- Testosterone (males only)
- Cortisol
- Estradiol
- Luteinizing hormone
- Calcitonin
- hematology (hemoglobin, hematocrit, RBC, mean cell volume, mean cell hemoglobin concentration, WBC, neutrophils [segmented], lymphocytes, monocytes, eosinophils, basophils, platelets)

The above lab measures will also be compared to reference range to determine whether they are abnormally high, low, or normal. The incidence and percent of high, low, and normal values will be summarized for each of the treatment arms and compared using the Fisher's exact test.

Shift tables of the change from maximum baseline to maximum postbaseline, from baseline to Week 26, and from baseline to Week 52 in the selected analytes using clinical meaningful thresholds will be summarized separately. The selected analytes include creatinine, ALT, AST, ACR, and calcitonin.

Similar analysis will be performed on the change from minimum baseline to minimum postbaseline, and the change from baseline to Week 26, and from baseline to Week 52 in eGFR, creatinine, ALT, AST, ACR, and calcitonin to that for the change from maximum baseline to maximum postbaseline.

Summary of pancreatic enzymes (p-amylase, amylase, lipase) by threshold ($>1\times$ upper limit of normal [ULN], $\geq 3\times$ ULN) from screening to Week 52 will be summarized descriptively using all ITT population, ITT population with normal range baseline, ITT population with $>1\times$ ULN baseline.

The number of patients and percentage of patients with a serum calcitonin ≥ 35 pg/mL and a simultaneous increase of 50% from baseline, and patients with a serum calcitonin ≥ 20 pg/mL and <35 pg/mL with a simultaneous increase 50% from baseline to Week 52 will be summarized using Fisher's exact test.

A summary of the number of patients and percentage of patients exceeding $2\times$, $3\times$, $5\times$, and $8\times$ ULN for each treatment at baseline, Week 26, and Week 52 will be presented for ALT, AST, and total bilirubin using Fisher's exact test.

A summary of the number of patients and percentage of patients meeting notable criteria for potential hepatotoxicity (ALT or AST $>3\times$ ULN and total bilirubin $>2\times$ ULN) for each treatment group at each postdose visit will be presented.

The number of patients and percentages for patients with pancreatic enzymes above ULN and greater than or equal to $3\times$ ULN will be summarized at baseline and by visit for each treatment group.

Number of patients and percentage for female patients showing positive outcome from serum pregnancy test will be summarized descriptively for each treatment group from baseline to Week 26, from Week 26 to Week 52, and from baseline to Week 52.

Number of patients and percentage of subjects of normal and abnormal values for each urinalysis test: protein, glucose, ketones, blood, and leukocyte esterase will be presented descriptively for each treatment group from baseline to Week 26 and from baseline to Week 52.

Additional analyses may be conducted if deemed necessary.

5.15.9. *Pubertal Progression Evaluation*

A shift table will be presented in those pubertal patients at baseline (Visit 2) to evaluate the change in Tanner Staging from baseline to Week 26, and baseline to Week 52 separately for male and female group at each treatment group without pooling. This includes no change and an increase in 1, 2, 3, and 4 levels. The likelihood ratio p-value will be the test statistic.

Morning serum hormone (estradiol, testosterone, LH, IGF-1, cortisol, and prolactin) will be analyzed with the method described in Section 5.15.8.

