9.3. Method of Assignment to Treatment

After the ICF and assent are signed and dated, a patient is considered “entered” in the study and will be assigned a patient number. Entered patients who meet all inclusion criteria and no exclusion criteria at screening will be randomized at Visit 2 (baseline). Patients who are randomized to the study treatment are “enrolled.” Patients will be randomized to 1 of 3 treatment arms (dulaglutide 0.75 mg/week, dulaglutide 1.5 mg/week, or placebo/week) at Visit 2 in a 1:1:1 ratio according to a computer generated random sequence using an IWRS. Patients will be stratified by HbA1c at Visit 1 (screening) (<8.0%, ≥8.0%), metformin use (“yes” versus “no”), and insulin use (“yes” versus “no”) to mitigate against confounding the effects of the treatments with severity of disease or treatment with these agents. The number of patients who are treated with lifestyle only and who are metformin naïve will be tracked, and when the number of these patients reaches approximately 25% of the total planned enrollment, IWRS will not allow further randomization of such patients. Site personnel will confirm that they have located the correct carton by entering a confirmation number found on the carton into the IWRS.

The second phase of the study is considered “open-label.” At 26 weeks, all patients on placebo will be dispensed 0.75 mg dulaglutide at that study visit assignment via the IWRS system. All patients previously on dulaglutide will continue on their previously assigned therapy.

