12.2.4. Concomitant Therapy

Patients using metformin and/or basal insulin will be allowed to enter the study and stay on their medication as a background therapy. Stratification will be used to ensure a balance across treatment arms of patients using these medications. These stratification factors will be included in all analysis models to further adjust the treatment effect estimates for background usage of metformin and/or insulin usage.

Concomitant medications, including previous therapy for diabetes, will be summarized by treatment. Frequencies will be analyzed using Fisher's exact test.

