12.2.9.3. Laboratory Analytes

Laboratory measurements will be listed by patient and visit.

Laboratory measurements will also be summarized. For continuous (numeric) laboratory analytes, the change from baseline to endpoint will be analyzed using an ANOVA on the rank-transformed data, with treatment as fixed effects. Last observation carried forward will be used to impute missing postbaseline values.

For subjective (qualitative) laboratory analytes, counts and percentages of patients with normal and abnormal values will be analyzed using Fisher's exact test.

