Unless otherwise specified, data listings will consist of all randomized patients. Both efficacy and safety analyses will be conducted using the ITT population. For safety except hypoglycemia analyses, all measurements including those made after taking rescue therapy will be included. Hypoglycemia analyses will be evaluated in the ITT population after censoring the data following administration of any rescue medication.

Unless otherwise specified, all tests of treatment effects will be conducted at a 2-sided alpha level of 0.05 and confidence intervals (CI) will be calculated at 95%, 2 sided.

For subgroup analyses, all tests of interactions between treatment and factors of interest will be conducted at a 2-sided alpha level of 0.10.

Visit 2 is the baseline visit. Baseline measurement for a corresponding parameter of interest is defined as the last nonmissing value taken prior to the first dosing of study drug. Baseline HbA1c value will be used to define HbA1c strata for analyses.

Unless otherwise specified, longitudinal continuous measures will be analyzed using MMRM with stratification factors (insulin usage [yes, no], metformin usage [yes, no], HbA1c strata [HbA1c: <8.0%, $\geq 8.0\%$]), treatment (Dula 1.5, Dula 0.75, Placebo or Placebo/Dula 0.75), visit, and treatment-by-visit as fixed effects, and corresponding baseline measurement as a covariate unless otherwise noted. The Kenward-Roger method will be used to estimate denominator degrees of freedom, and the REML approach to obtain model estimate. An unstructured covariance structure will be used to model the within-patient errors. If this model fails to converge, the following covariance structures will be tested in order:

- Toeplitz with heterogeneity
- Autoregressive with heterogeneity, by visit
- Compound symmetry with heterogeneous variances, by visit
- Toeplitz
- Autoregressive
- Compound symmetry without heterogeneous variances, by visit

The first variance-covariance structure that converges will be used.

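### The rank ANOVA of laboratory changes has treatment as its only term, without a baseline covariate or the stratification factors that the protocol says go in all analysis models

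*SAP*

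**What the plan says.** SAP 5.15.8 lists the continuous analytes and says: "For each continuous laboratory measurement listed below, the change from baseline will be summarized for each treatment". It then gives the test: "These analytes will be analyzed using ANOVA on the ranks, with treatment as a fixed effect". That sentence does not itself say whether the ranks are of changes or of raw values. Protocol 12.2.9.3 does: "the change from baseline to endpoint will be analyzed using an ANOVA on the rank-transformed data, with treatment as fixed effects". Neither section names any other model term.

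Protocol 12.2.4, on metformin and insulin background use, sets a general rule: "These stratification factors will be included in all analysis models to further adjust the treatment effect estimates". Protocol 9.3 stratifies randomisation by these two factors and by screening HbA1c (<8.0%, ≥8.0%).

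The SAP default in Section 5.2 is fuller: "Unless otherwise specified, longitudinal continuous measures will be analyzed using MMRM with stratification factors", with the corresponding baseline as a covariate. Vital signs and ECG (SAP 5.15.6 and 5.15.7) use models with strata and baseline. The hypoglycemia rate model (5.15.2.1) includes the stratification factors. Effects on pancreatic enzymes and serum calcitonin are named in the secondary safety objectives (Protocol 6.2, SAP 4.2).

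**The concern.** Two things look wrong.

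The first is consistency. The laboratory test is an analysis model, and it omits factors that the protocol says every analysis model will contain. No reason is given for the exception. Skewness is a reason to use ranks, but ranked baseline and strata fit in the same rank model.

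The second is efficiency. A change score with no baseline covariate is less precise than the covariate-adjusted comparison unless baseline and endpoint are almost perfectly correlated. It also carries chance baseline differences into the comparison: the arm that starts higher by luck tends to fall more. With about 50 patients per arm, and a purpose of detecting unwanted shifts, lost sensitivity works against the safety objective.

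**Working it through.** **The plan's own figure.** The only power figures are for HbA1c (SAP 5.1): difference 0.65, SD 1, 120 completers, so 80 pooled against 40 placebo. SE = √(1/80 + 1/40) = 0.1936; 0.65/0.1936 − 1.96 = 1.40; power 91.9%, against a stated minimum of 90%. For a single arm (40 v 40), power is 82.8%, against a stated minimum of 80%. Both reproduce. No such figure exists for any laboratory analyte.

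**Inputs.** From the documents: 50 per arm, 1:1:1 allocation, two-sided 0.05, pooled contrast (100 v 50). Assumed: rho, the shift, the SD and the shape of the distribution.

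**Precision, normal theory.** With equal variances s² at both times, Var(change) = 2s²(1 − rho) and Var(baseline-adjusted) = s²(1 − rho²), so the ratio is (1 + rho)/2. Take an effect that gives 80% power on change scores, where the standardised effect is 1.96 + 0.84 = 2.80. At rho 0.5 it becomes 2.80/√0.75 = 3.23, and power is Φ(3.23 − 1.96) = 90%.

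| rho | variance ratio | power, change only | power, adjusted |
|---|---|---|---|
| 0.3 | 0.65 | 80% | 93.5% |
| 0.5 | 0.75 | 80% | 89.9% |
| 0.7 | 0.85 | 80% | 86.0% |
| 0.9 | 0.95 | 80% | 82.0% |

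This is for unranked normal data, so it bounds what ranks are likely to deliver.

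**Precision, the planned rank test.** Simulation of the rank ANOVA on change, treatment only, against the adjusted rank model; lognormal data, assumed shift 0.45 SD on the log scale, 3,000 runs per cell:

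| rho | log-SD 0.5 | log-SD 1.0 |
|---|---|---|
| 0.3 | 58% to 70% | 57% to 66% |
| 0.5 | 72% to 79% | 69% to 73% |
| 0.7 | 91% to 92% | 88% to 88% |

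Separate runs gave 56–58% rising to 65–72% at rho 0.3, and 70–71% rising to 75–81% at rho 0.5. Across all shapes tried, the gain is about 9–15 points at rho 0.3, 4–10 at 0.5 and 0–4 at 0.7. At 0.9, with an assumed shift of 0.27 SD, power is essentially unchanged and at worst about 1 point is lost. The gain shrinks as skewness grows. Adding the HbA1c stratum as a further, non-prognostic factor left these results within about 1 point.

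**Type I error.** With no treatment effect, the treatment-only test rejected in 4.7–5.5% of runs, and the adjusted test was also near 5%.

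**Chance imbalance.** The pooled-minus-placebo difference in baseline means has SE √(1/100 + 1/50) = 0.173 SD. A difference of at least 0.25 SD is 1.44 SE, so it occurs in about 15% of trials for any one analyte. SAP 5.15.8 lists 39 analytes (3 pancreatic, 7 liver, 6 renal, 4 lipid, 7 hormone, 12 hematology), so about 39 × 0.15 ≈ 6 such imbalances are expected. At rho 0.5, a 0.25 SD imbalance moves the expected difference in change by (1 − 0.5) × 0.25 = 0.125 SD, or 0.72 of the SE of the change comparison (√1 × 0.173). Among simulated null trials with an imbalance of at least 0.25 SD, the unadjusted test rejected in about 14% at rho 0.5, 9–12% at 0.7 and 6% at 0.9, against about 3–7% when adjusted.

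**Strata alone.** With an assumed 0.5 SD insulin effect and rho 0.7, the treatment-only test was conservative (4.0%), and adding the strata without baseline moved power from 74% to 76%.

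**The case against.** The strongest reply is that the choice is pre-specified, agrees between protocol and SAP, and controls type I error. The Section 5.2 default yields where another method is specified, and treatment-only safety tests occur elsewhere (the exposure ANOVA, Fisher's tests for adverse events). No laboratory endpoint is in the H1–H12 testing scheme or the sample-size basis. The rank p-value is also one output among many: high/low/normal incidence, shift tables, enzyme and calcitonin thresholds, adjudicated pancreatitis and thyroid events. All of this stands, and it limits the weight of the point.

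A reader might infer that the baseline value is thrown away. The documents do not support that. It is subtracted to form every change score, and is used again in the within-arm signed-rank tests, the shift tables, the calcitonin 50%-increase criteria and the enzyme summaries split by baseline level. What is missing is adjustment for it.

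It is also fair to say that the gain rests on figures the documents do not give, and that at high correlation or strong skew it vanishes. That stands too.

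None of this answers Protocol 12.2.4. Its rule covers all analysis models, and the laboratory model does not follow it. Strata add little power on their own, but the two texts still disagree.

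**Conclusion.** The point holds as one of precision and internal consistency. The laboratory model omits baseline as a covariate and the stratification factors, and the second omission contradicts Protocol 12.2.4. The cost ranges from about 15 power points at rho 0.3 to nothing at 0.9. It rests on assumed correlation, shift and distribution shape, with 50 per arm and the pooled contrast. Results for individual analytes are also exposed to chance baseline imbalance.

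Two stronger inferences fail. The conditional rejection rates of 6–14% do not mean the test is invalid: they apply only to trials with an unlucky baseline, and the overall rate stays near 5%. Nor do they show that a real enzyme or calcitonin effect would go unseen, given the threshold, shift and event summaries. No primary or multiplicity-controlled conclusion changes. The improvement is worth making because the extra terms are already collected and adding them costs at most about 1 power point in the cases tried.

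**What to change.** In SAP 5.15.8, state that the ranked response is change from baseline. Add ranked baseline, insulin use, metformin use and HbA1c stratum (<8.0%, ≥8.0%, defined from baseline HbA1c as in SAP 5.2) to the rank model. Keep the pooled and single-dose contrasts against placebo. Align Protocol 12.2.9.3 and the matching sentence in the synopsis. Protocol 12.2.1 lets a change that does not touch a principal feature be made and justified in a revised SAP.

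If the sponsor prefers the treatment-only model, narrow Protocol 12.2.4 so that it names the models it covers and no longer says all of them.

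The cost is a few lines of text and one model statement. No new data and no extra patients are needed.
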